### 12.10.3. Examples of Strong and Moderate CYP3A4 Inhibitors

Refer to [Section 10.13](#).

### 12.10.4. Recommended Dose Modifications for Encorafenib-related\* Adverse Events and Overlapping Toxicities with Sasanlimab\*\*

Severity of Adverse Event	Dose Modifications
New Primary Malignancies	
RAS mutation-positive malignancies	Permanently discontinue encorafenib and binimetinib.
Uveitis	
Grade 1-3	
Consult ophthalmologist. Treat with topical steroids such as 1% prednisolone acetate suspension and iridocyclitics as appropriate.
 
If considered to be immune-related AE,
 
 
• Grade 1: continue sasanlimab
 
• Grade 2: hold sasanlimab with treatment guided by ophthalmologist with or without systemic corticosteroids
 
• Grade 3: permanently discontinue sasanlimab with treatment guided by ophthalmologist on systemic corticosteroids.
 
 
If Grade 1 or 2 uveitis considered to be encorafenib related and does not respond to specific ocular therapy, or for Grade 3 uveitis, withhold encorafenib and binimetinib for up to 6 weeks.
 
 
• If improved, resume at same or reduced dose.
 
• If not improved, permanently discontinue.
 

Grade 4	Permanently discontinue sasanlimab, encorafenib, and binimetinib.

Severity of Adverse Event	Dose Modifications
Other Eye Disorders (i.e., non-Uveitis Events)	
Grade 1–2	Maintain dose level of encorafenib and binimetinib and increase frequency of ophthalmic monitoring to at least every 14 days until stabilization or resolution.  If considered irAE, refer to Uveitis management above.
Grade 3	Interrupt dosing of encorafenib and binimetinib and refer participant to ophthalmologist within 7 days. 
 
• If resolved to Grade <math>\leq 1</math> in <math>\leq 21</math> days, resume treatment at 1 reduced dose level of encorafenib and binimetinib.
 
• If not resolved to Grade <math>\leq 1</math> in <math>\leq 21</math> days, permanently discontinue encorafenib and binimetinib and close follow-up with ophthalmic monitoring until stabilization or resolution.
 
• If considered irAE, refer to Uveitis management above.
 

Grade 4	Permanently discontinue sasanlimab, encorafenib, and binimetinib and immediate follow-up with ophthalmic monitoring until stabilization or resolution.
QTc Prolongation	
QTcF $>500$ msec and $\leq 60$ msec increase from baseline	1 st occurrence: 
 
• Temporarily interrupt dosing of encorafenib until QTcF <math><500</math> msec. Then resume treatment at 1 reduced dose level of encorafenib.
 
 2 nd occurrence: 
 
• Temporarily interrupt dosing of encorafenib treatment until QTcF <math><500</math> msec. Then resume treatment at 1 reduced dose level of encorafenib.
 
 3 rd occurrence: 
 
• Permanently discontinue encorafenib and binimetinib.
 

QTcF $>500$ msec and $>60$ msec increase from baseline	Permanently discontinue encorafenib and binimetinib.
Hepatotoxicity	
Grade 2 AST or ALT increased	Maintain encorafenib dose. 
 
• If no improvement within 4 weeks, withhold encorafenib until improved to Grade 0-1 or
 

Severity of Adverse Event	Dose Modifications
	
to pretreatment/baseline levels and then resume at the same dose.
 
Refer to Sections 6.6 and 10.10 if considered irAE.

Grade 3 or 4 AST or ALT increased	
See Other Adverse Reactions in this table for guidance on encorafenib and binimetinib. Permanently discontinue sasanlimab.
 
See Sections 6.6 and 10.10 for irAE.

Dermatologic (Except Palmar-plantar Erythrodysesthesia Syndrome)	
Grade 2	
If no improvement within 2 weeks, withhold until Grade 0-1. Resume at same dose if first occurrence or reduce dose if recurrent.
 
Refer to Sections 6.6 and 10.10 if considered irAE.

Grade 3	
Withhold until Grade 0-1. Resume at same dose if first occurrence or reduce dose if recurrent.
 
Refer to Sections 6.6 and 10.10 if considered irAE.

Grade 4	
Permanently discontinue sasanlimab, encorafenib, and binimetinib. Refer to Sections 6.6 and 10.10 if considered irAE.

Hand-foot Skin Reaction (HFSR)/Palmar-plantar Erythrodysesthesia Syndrome (Dose Adjustment for Encorafenib ONLY)	
Grade 1	
Maintain dose of encorafenib. Promptly institute supportive measures, such as topical therapy, for symptomatic relief. Give instruction on life-style modifications.

Grade 2	
1st occurrence:
 
 
• Maintain dose of encorafenib and HFSR should be closely monitored. Promptly institute supportive measures, such as topical therapy, for symptomatic relief. Give instruction on life-style modifications.
 
• If no improvement <math>\leq 14</math> days, interrupt dosing of encorafenib until resolved to Grade <math>\leq 1</math>. Resume treatment with encorafenib at current dose level. Continue supportive measures, such as topical therapy, for symptomatic relief. Give instruction on life-style modifications.
 

Severity of Adverse Event	Dose Modifications
	
Additional occurrence:
 
 
Treatment with encorafenib may be maintained or interrupted based upon the investigator's discretion. Continue supportive measures, such as topical therapy, for symptomatic relief. Give instruction on life-style modifications.
 
 
If interrupted dosing of encorafenib per investigator's judgment, interrupt until resolved to Grade <math>\leq</math>1. Resume treatment with encorafenib at the same dose level or 1 reduced dose level based upon the investigator's discretion.

Grade 3	
1st or 2nd occurrence:
 
 
Interrupt dosing of encorafenib until resolved to Grade <math>\leq</math>1. Promptly initiate supportive measures, such as topical therapy, for symptomatic relief. Give instruction on life-style modifications. Reassess the participant weekly. Then resume treatment at 1 reduced dose level of encorafenib.
 
Consider referral to dermatologist and manage HFSR per dermatologist's recommendation.
 
 
>3rd occurrence:
 
 
Interrupt dosing of encorafenib until resolved to Grade <math>\leq</math>1, decision to resume treatment with encorafenib at 1 reduced dose level or permanently discontinue encorafenib should be based upon the investigator's discretion.
 

Nausea/Vomiting	
Grade 1-2	Maintain dose level of encorafenib and binimetinib. Promptly institute antiemetic measure.
Grade 3	
Interrupt dosing of encorafenib and binimetinib until resolved to Grade <math>\leq</math>1. Resume treatment at 1 reduced dose level of encorafenib. Resume treatment with binimetinib at the current dose if, in the judgment of the investigator, the toxicity is considered to be unrelated to binimetinib, or at 1 reduced dose level.
 
Note: Interrupt dosing of encorafenib and binimetinib for <math>\geq</math>Grade 3 vomiting or Grade 3 nausea only if the vomiting or nausea cannot be controlled with optimal antiemetics (as per local practice).

Severity of Adverse Event	Dose Modifications
Grade 4	Permanently discontinue encorafenib and binimetinib.
Other Adverse Reactions (including renal, hemorrhage)	
Recurrent Grade 2 or First occurrence of any Grade 3	Withhold for up to 4 weeks. 
 
• If improves to Grade 0-1 or to pretreatment/baseline levels, resume at reduced dose.
 
• If no improvement, permanently discontinue encorafenib and binimetinib.
 

First occurrence of any Grade 4	Permanently discontinue or withhold for up to 4 weeks. 
 
• If improves to Grade 0-1 or to pretreatment/baseline levels, then resume at a reduced dose.
 
• If no improvement, permanently discontinue encorafenib and binimetinib.
 

Recurrent Grade 3	Consider permanently discontinuing encorafenib and binimetinib.
Recurrent Grade 4	Permanently discontinue encorafenib and binimetinib.

\*For adverse events that may be related to both encorafenib and binimetinib, guidance is provided for the other agent also.

\*\* Refer to [Section 12.6.6](#) for management of potential overlapping toxicities. Any adverse event suspected to be immune-related should be managed accordingly as in [Sections 6.6](#) and [10.10](#). Consult appropriate specialist as indicated.

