### 12.10.5. Recommended Dose Modifications for Binimetinib-related\* Adverse Events and Overlapping Toxicities with Sasanlimab\*\*

Severity of Adverse Event	Dose Modifications
Cardiomyopathy	
Asymptomatic, absolute decrease in LVEF of >10% from baseline that is also below the LLN	
Withhold binimetinib for up to 4 weeks, evaluate LVEF every 2 weeks.
 
Resume binimetinib at a reduced dose if the following are present:
 
 
• LVEF is at or above the LLN and
 
• Absolute decrease from baseline is 10% or less and
 
• Participant is asymptomatic.
 
 
If LVEF does not recover within 4 weeks permanently discontinue binimetinib.
 
Consult cardiologist to rule out immune-related myocarditis, see Section 10.10.

Grade 3-4 (Symptomatic congestive heart failure or absolute decrease in LVEF of >20% from baseline that is also below LLN)	
Permanently discontinue binimetinib. Closely monitor LVEF until resolution or up to 16 weeks.
 
Consult cardiologist to rule out immune-related myocarditis, see Section 10.10.

Venous Thromboembolism	
Uncomplicated DVT or PE	
Withhold binimetinib.
 
 
• If improves to Grade 0-1, resume at a reduced dose.
 
• If no improvement, permanently discontinue binimetinib.
 

Life threatening PE	Permanently discontinue binimetinib.
Serous Retinopathy	
Symptomatic serous retinopathy/ Retinal pigment epithelial detachments	
Withhold binimetinib for up to 10 days.
 
 
• If improves and becomes asymptomatic, resume at the same dose.
 
• If not improved, resume at a lower dose level or permanently discontinue binimetinib.
 

Retinal Vein Occlusion (RVO)	
Any Grade	Permanently discontinue binimetinib.
Uveitis	
Grade 1-3	
Consult ophthalmologist. Treat with topical steroids such as 1% prednisolone acetate suspension and iridocyclitics as appropriate.
 
If considered to be immune-related AE,

Severity of Adverse Event	Dose Modifications

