Recurrent Grade 2 or First occurrence of any Grade 3	
Withhold for up to 4 weeks.
 
 
• If improves to Grade 0-1 or to pretreatment/baseline levels, resume at reduced dose.
 
• If no improvement, permanently discontinue binimetinib and encorafenib.
 

First occurrence of any Grade 4	
Permanently discontinue or withhold for up to 4 weeks.
 
 
• If improves to Grade 0-1 or to pretreatment/baseline levels, then resume at a reduced dose.
 
• If no improvement, permanently discontinue binimetinib and encorafenib.
 

Recurrent Grade 3	Consider permanently discontinuing binimetinib and encorafenib.
Recurrent Grade 4	Permanently discontinue binimetinib and encorafenib.

\*For adverse events that may be related to both binimetinib and encorafenib, guidance is provided for the other agent also.

\*\* Refer to Section 12.6.6 for management of potential overlapping toxicities. Any adverse event suspected to be immune-related should be managed accordingly as in Sections 6.6 and 10.10. Consult appropriate specialist as indicated.

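### Sub-Study A: for a retinal event attributed to both encorafenib and binimetinib, the general eye row in Section 12.10.4 contradicts the specific retinal rows in Section 12.10.5 on binimetinib dosing

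*Protocol*

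**What the plan says.** Section 12.10.4 covers encorafenib-related events. Its row "Other Eye Disorders (i.e., non-Uveitis Events") gives one instruction per grade band, and each names binimetinib:

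- Grade 1-2: "Maintain dose level of encorafenib and binimetinib and increase frequency of ophthalmic monitoring to at least every 14 days".
- Grade 3: interrupt both drugs. If the event falls to Grade 1 or less within 21 days, "resume treatment at 1 reduced dose level of encorafenib and binimetinib"; otherwise stop both permanently.
- Grade 4: "Permanently discontinue sasanlimab, encorafenib, and binimetinib and immediate follow-up with ophthalmic monitoring until stabilization or resolution".

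Section 12.10.5 covers binimetinib-related events and has two specific retinal rows:

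- RVO, any grade: "permanently discontinue binimetinib".
- "Symptomatic serous retinopathy/ Retinal pigment epithelial detachments", with no grade stated: hold binimetinib for at most 10 days. Restart at the same dose if the event improves and symptoms clear; if not, restart lower or stop.

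The residual eye row in 12.10.5 excludes both retinal events and uveitis. The one in 12.10.4 excludes only uveitis.

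Each table extends itself to the other drug by footnote. Section 12.10.4 says "For adverse events that may be related to both encorafenib and binimetinib, guidance is provided for the other agent also", and Section 12.10.5 says "For adverse events that may be related to both binimetinib and encorafenib, guidance is provided for the other agent also". Section 12.6.6.2 points to both tables without ranking them.

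**The concern.** The two tables should give one binimetinib instruction for one event. A retinal event judged possibly related to both drugs falls under the general row in 12.10.4 and also under a specific row in 12.10.5.

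A site that applied 12.10.4 as written could keep or restart binimetinib in an RVO that 12.10.5 treats as the end of binimetinib. It could also dose through symptomatic serous retinopathy that 12.10.5 would hold. In the other direction, a Grade 3 serous event that clears quickly would lead to a binimetinib reduction under 12.10.4, and Section 12.6.6.2 does not allow re-escalation after a reduction for ocular toxicity of Grade 2 or higher.

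**Working it through.** There is no plan figure to reproduce, so the check compares the two tables row by row for binimetinib.

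| Event | Section 12.10.4 | Section 12.10.5 | Result |
|---|---|---|---|
| RVO, Grade 1-2 | maintain | permanent stop | conflict |
| RVO, Grade 3 | interrupt; one level lower if Grade 1 or less within 21 days, otherwise stop | permanent stop | conflict |
| RVO, Grade 4 | permanent stop | permanent stop | agree |
| Symptomatic serous retinopathy/RPED, Grade 1-2 | maintain | hold up to 10 days | conflict |
| Same, Grade 3, cleared within 10 days | one level lower | same dose | conflict |
| Same, Grade 4 | permanent stop | hold; restart possible | conflict |
| Asymptomatic serous retinopathy | general row applies | no specific row | no conflict |

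**Is there a tie-breaker?** Four candidates were checked.

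- *Causality.* Section 6.6 assigns modifications to each product by causality where possible, and Section 12.6.6.1 asks the physician to identify the responsible component. Neither settles an event attributed to both drugs.
- *Worst preceding toxicity* (Section 12.6.6.2). This fixes the grade, not the table.
- *Labeled or institutional guidance* (Sections 12.6.6.1 and 12.6.6.2). This points outside the protocol and ranks neither table.
- *The footnotes.* They mirror each other and set no order.

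**Dose consequence of the Grade 3 serous case.** Using Table 10:

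- From 45 mg BID, 12.10.5 restarts at 45 mg and 12.10.4 at 30 mg: (45 − 30)/45 = 33% lower.
- From 30 mg BID (dose level −1), the restart doses are 30 mg and 15 mg: (30 − 15)/30 = 50% lower.

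**How many events.** Inputs: 62 Phase 2 participants (Section 12.4.2), and the rates in Section 12.2.2.1, which are 0.1% for RVO (pooled BRAF-mutant melanoma trials) and 8% for symptomatic serous retinopathy. Carrying these melanoma rates over to NSCLC is an assumption.

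- RVO: 62 × 0.001 = 0.062 expected events; chance of at least one = 1 − 0.999^62 = 0.060.
- Symptomatic serous retinopathy: 62 × 0.08 = 4.96 expected events. If the true rate were 4% or 12%, the figure would be 62 × 0.04 = 2.48 or 62 × 0.12 = 7.44.

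These are counts of events, not of misdosed participants. A wrong dose also needs attribution to both drugs and use of the general row over the specific one. The protocol gives no figure for either.

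**The case against.** The best defense is that the protocol treats these retinal events as belonging to binimetinib. Section 12.2.2.1 calls serous retinopathy and RVO class effects of MEK inhibitors. The RVO and serous retinopathy rows in 12.10.5 name binimetinib only, whereas neighboring rows such as uveitis and nausea/vomiting also instruct on encorafenib. A site that goes by causality, or prefers a row named for the event over a residual one, ends in 12.10.5. Both tables are headed as recommendations. Labeled guidance and specialist consultation apply as well. Section 12.8.2.3 requires extra imaging when a retinal abnormality is suspected, and exclusion criterion 21 keeps out participants with prior RVO or current risk factors.

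Most of this stands. It makes the wrong reading unlikely, and that limits the severity. It does not supply a rule. The general row in 12.10.4 names binimetinib and leaves out the retinal exclusion that its counterpart carries. Preferring the specific row also does not settle Grade 4 serous retinopathy: that row has no grade limit and allows a restart, while both tables stop binimetinib permanently for other Grade 4 eye disorders.

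A reader might also infer from Section 12.2.3 that the protocol itself expects ocular toxicity to be shared by encorafenib and binimetinib. It does not say that. The overlap discussed there is between the encorafenib/binimetinib pair and PD-1 inhibition, so it does not support attribution to both targeted drugs.

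**Conclusion.** The two tables contradict each other for RVO of Grade 1-3 and for symptomatic serous retinopathy/RPED at every grade, but only when the event is attributed to both drugs. The sharpest case is RVO of Grade 1-2, where one table maintains binimetinib and the other ends it.

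A reader might infer that the protocol directs sites to continue binimetinib through RVO, or that a meaningful number of participants will be misdosed. The documents support neither. The specific row plainly ends binimetinib in RVO, and most sites would probably follow it. The number of participants who would receive a wrong dose cannot be estimated. RVO itself is about 0.06 expected events in 62 if the melanoma rate holds, and the roughly 5 expected symptomatic serous events are only a pool in which the conflict could arise.

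Endpoints, DLT rules and sample size are unaffected. This is a minor safety-text correction.

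**What to change.** Keep the 12.10.4 row and add to it: *For retinal vein occlusion and for symptomatic serous retinopathy/RPED of Grade 1-3, binimetinib follows the specific rows in Section 12.10.5, except that binimetinib is also permanently discontinued whenever encorafenib is permanently discontinued (Section 12.6.6.1); Grade 4 follows this row.*

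The exception is needed. If a Grade 3 serous event has not resolved by 21 days, 12.10.4 stops encorafenib permanently, and Section 12.6.6.1 then requires binimetinib to stop too. The 12.10.5 row alone could still allow a lower binimetinib dose.

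In 12.10.5, limit the serous retinopathy row to Grade 1-3 and add: *Grade 4: permanently discontinue binimetinib.* Do not add a stop of sasanlimab or encorafenib there, since that would create a new rule for events attributed to binimetinib alone.

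Adding a non-retinal qualifier to the 12.10.4 row label would be shorter, but it would remove that row's encorafenib instruction and its Grade 4 stop of all three drugs for retinal events.

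The clinical team should confirm two consequences. Grade 4 serous retinopathy would now end binimetinib even when attributed to binimetinib alone. After a Grade 3 event attributed to both drugs that clears within 10 days, encorafenib would restart one level lower and binimetinib at the same dose.

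Cost: one sentence in 12.10.4, and one grade limit and one line in 12.10.5, in the next amendment. No new data, visits or participants are needed.

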### 12.10.5. Recommended Dose Modifications for Binimetinib-related\* Adverse Events and Overlapping Toxicities with Sasanlimab\*\*

Severity of Adverse Event	Dose Modifications
Cardiomyopathy	
Asymptomatic, absolute decrease in LVEF of >10% from baseline that is also below the LLN	
Withhold binimetinib for up to 4 weeks, evaluate LVEF every 2 weeks.
 
Resume binimetinib at a reduced dose if the following are present:
 
 
• LVEF is at or above the LLN and
 
• Absolute decrease from baseline is 10% or less and
 
• Participant is asymptomatic.
 
 
If LVEF does not recover within 4 weeks permanently discontinue binimetinib.
 
Consult cardiologist to rule out immune-related myocarditis, see Section 10.10.

Grade 3-4 (Symptomatic congestive heart failure or absolute decrease in LVEF of >20% from baseline that is also below LLN)	
Permanently discontinue binimetinib. Closely monitor LVEF until resolution or up to 16 weeks.
 
Consult cardiologist to rule out immune-related myocarditis, see Section 10.10.

Venous Thromboembolism	
Uncomplicated DVT or PE	
Withhold binimetinib.
 
 
• If improves to Grade 0-1, resume at a reduced dose.
 
• If no improvement, permanently discontinue binimetinib.
 

Life threatening PE	Permanently discontinue binimetinib.
Serous Retinopathy	
Symptomatic serous retinopathy/ Retinal pigment epithelial detachments	
Withhold binimetinib for up to 10 days.
 
 
• If improves and becomes asymptomatic, resume at the same dose.
 
• If not improved, resume at a lower dose level or permanently discontinue binimetinib.
 

Retinal Vein Occlusion (RVO)	
Any Grade	Permanently discontinue binimetinib.
Uveitis	
Grade 1-3	
Consult ophthalmologist. Treat with topical steroids such as 1% prednisolone acetate suspension and iridocyclitics as appropriate.
 
If considered to be immune-related AE,

Severity of Adverse Event	Dose Modifications
	
Grade 1: continue sasanlimab.
 
Grade 2: hold sasanlimab with treatment guided by ophthalmologist with or without systemic corticosteroids.
 
Grade 3: permanently discontinue sasanlimab with treatment guided by ophthalmologist on systemic corticosteroids.
 
If Grade 1 or 2 considered to be binimetinib related and does not respond to specific ocular therapy, or for Grade 3 uveitis, withhold binimetinib and encorafenib for up to 6 weeks.
 
 
• If improved, resume at same or reduced dose.
 
• If not improved, permanently discontinue binimetinib.
 

Grade 4	Permanently discontinue binimetinib and sasanlimab.
Other Eye Disorders (ie, Non-retinal Events, non-Uveitis Events)	
Grade 1-2	
Maintain dose level of encorafenib and binimetinib and increase frequency of ophthalmic monitoring to at least every 14 days until stabilization or resolution.
 
If considered irAE, refer to Uveitis management above.

Grade 3	
Interrupt dosing of encorafenib and binimetinib and refer participant to ophthalmologist within 7 days.
 
 
• If resolved to Grade <math>\leq 1</math> in <math>\leq 21</math> days, resume treatment at 1 reduced dose level of encorafenib and binimetinib.
 
• If not resolved to Grade <math>\leq 1</math> in <math>\leq 21</math> days, permanently discontinue encorafenib and binimetinib and close follow-up with ophthalmic monitoring until stabilization or resolution.
 
 
If considered irAE, refer to Uveitis management above.

Grade 4	Permanently discontinue sasanlimab, encorafenib, and binimetinib and immediate follow-up with ophthalmic monitoring until stabilization or resolution.
Interstitial Lung Disease	
Grade 1	Consider withholding sasanlimab if considered irAE, see Section 10.10 .
Grade 2	Withhold binimetinib for up to 4 weeks.

Severity of Adverse Event	Dose Modifications
	
 
If improved to Grade 0-1, resume at a reduced dose.
 
If not resolved within 4 weeks, permanently discontinue.
 
 Withhold Sasanlimab if considered irAE, see Section 10.10 .
Grade 3 or Grade 4	Permanently discontinue binimetinib and sasanlimab. See Section 10.10 if considered irAE.
Hepatotoxicity	
Grade 2 AST or ALT increased	Maintain binimetinib dose. 
 
If no improvement within 2 weeks, withhold binimetinib until improved to Grade 0-1 or to pretreatment/baseline levels and then resume at the same dose.
 
 Refer to Sections 6.6 and 10.10 if considered irAE.
Grade 3 or 4 AST or ALT increased	See Other Adverse Reactions in this table for guidance on encorafenib and binimetinib. Permanently discontinue sasanlimab. See Sections 6.6 and 10.10 for irAE.
Rhabdomyolysis or Creatine Phosphokinase (CPK) elevations	
Grade 4 asymptomatic CPK elevation or Any Grade CPK elevation with symptoms or with renal impairment	Withhold binimetinib dose for up to 4 weeks. 
 
If improved to Grade 0-1 resume at a reduced dose.
 
If not resolved within 4 weeks, permanently discontinue binimetinib.
 

Dermatologic	
Grade 2	If no improvement within 2 weeks, withhold until Grade 0-1. Resume at same dose if first occurrence or reduce dose if recurrent.
Grade 3	Withhold until Grade 0-1. Resume at same dose if first occurrence or reduce dose if recurrent.
Grade 4	Permanently discontinue binimetinib and encorafenib.
Nausea/Vomiting	
Grade 1-2	Maintain dose level of encorafenib and binimetinib. Promptly institute antiemetic measure.

Severity of Adverse Event	Dose Modifications
Grade 3	
Interrupt dosing of encorafenib and binimetinib until resolved to Grade <math>\leq</math>1. Then resume treatment at 1 reduced dose level of encorafenib. Resume treatment with binimetinib at the current dose if, in the judgment of the investigator, the toxicity is considered to be unrelated to binimetinib, or at 1 reduced dose level.
 
Note: Interrupt dosing of encorafenib and binimetinib for <math>\geq</math>Grade 3 vomiting or Grade 3 nausea only if the vomiting or nausea cannot be controlled with optimal antiemetics (as per local practice).
 
If unresolved permanently discontinue binimetinib and encorafenib.

Grade 4	Permanently discontinue binimetinib and encorafenib.
Other Adverse Reactions. Refer to Sections 6.6 and 10.10 if considered irAE	
Recurrent Grade 2 or First occurrence of any Grade 3	
Withhold for up to 4 weeks.
 
 
• If improves to Grade 0-1 or to pretreatment/baseline levels, resume at reduced dose.
 
• If no improvement, permanently discontinue binimetinib and encorafenib.
 

First occurrence of any Grade 4	
Permanently discontinue or withhold for up to 4 weeks.
 
 
• If improves to Grade 0-1 or to pretreatment/baseline levels, then resume at a reduced dose.
 
• If no improvement, permanently discontinue binimetinib and encorafenib.
 

Recurrent Grade 3	Consider permanently discontinuing binimetinib and encorafenib.
Recurrent Grade 4	Permanently discontinue binimetinib and encorafenib.

\*For adverse events that may be related to both binimetinib and encorafenib, guidance is provided for the other agent also.

\*\* Refer to Section 12.6.6 for management of potential overlapping toxicities. Any adverse event suspected to be immune-related should be managed accordingly as in Sections 6.6 and 10.10. Consult appropriate specialist as indicated.

